4.1.4.2 Screening AKI and Screening eGFR

Screening (pre-dose) AKI will be determined by comparing screening (pre-dose) creatinine to the algorithmic determination of reference as described in Exhibit 1 based on the rules summarized in Exhibit 2.

Exhibit 2. Algorithmic Determination of Screening (pre dose) AKI Stage						
Stage	Serum Creatinine					
0	<1.5 times reference					
1	1 1.5 to <2.0 times reference					
2 ≥2 to 3 times reference						
3	≥ 3 times reference OR Increase in serum creatinine to ≥4 mg/dL OR Initiation of renal replacement therapy					
Reference may be either algorithmically determined or independently adjudicated depending on analysis.						

Screening eGFR will be determined using the following formula.

Screening eGFR (mL/min/1.73 m²) = $175 \times (Screening Cr)^{-1.154} \times (Age)^{-0.203} \times (0.742 if female) \times (1.212 if African American).$

As a sensitivity analysis, when determining AKI endpoints, the adjudicated reference creatinine will be used in place of the algorithmically determined reference value.

4.1.4.3 Day 28 eGFR

Day 28 eGFR will be determined by converting Day 28 creatinine to Day 28 eGFR using the following formula:

Day 28 eGFR (mL/min/1.73 m²) = $175 \times (\text{Cr Day } 28)^{-1.154} \times (\text{Age})^{-0.203} \times (0.742 \text{ if female}) \times (1.212 \text{ if African American}).$

Percentage loss in eGFR at Day 28 will be determined using the following formula.

Percentage loss in eGFR at Day 28 = 100% times [Screening eGFR - (Day 28 eGFR) / Screening eGFR]. If percentage loss $\geq 37\%$ then patient fails key secondary endpoint.

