2.3 Key Secondary AKI Endpoint

The same endpoint that is being currently employed in the ongoing ATB-203 study of AKI in sepsis will be evaluated as the key secondary endpoint in this study. The key secondary endpoint is *freedom from durable loss of renal function at Day 28*. Only subjects with AKI Stage 2 or Stage 3 prior to initial drug dosing will be included in this comparison. The key secondary endpoint requires:

- (i) Alive at Day 28,
- (ii) Free of dialysis at Day 28, and
- (iii) Less than a 37% loss of estimated Glomerular Filtration Rate (eGFR; measured with the Modification of Diet in Renal Disease (MDRD) formula from the patient's reference eGFR)) at Day 28.

Reference creatinine values, baseline AKI stage and percentage loss of eGFR at Day 14 and 28 will be determined through algorithmic determination (see details below). Percentage loss of eGFR determined algorithmically will be based on a comparison of eGFR at screening compared to an algorithmically determined reference creatinine value. A sensitivity analysis will utilize an independently adjudicated reference value to determine baseline eGFR.

To control type 1 error for the key secondary efficacy endpoint, superiority of Reltecimod relative to placebo in terms of freedom from durable loss of renal function at Day 28 among those presenting with Stage 2 or Stage 3 AKI will only be interpreted as a confirmatory hypothesis test if $p \le 0.01$ for the primary endpoint (NICCE) and $p \le 0.05$ for the co-primary endpoint (CCPE).

Otherwise, treatment group comparisons in terms of the key secondary efficacy (AKI) endpoint will be interpreted as a descriptive endpoint. An unadjusted chi-square test using a two-sided type 1 error of α =0.05 will be used to test superiority of Reltecimod relative to placebo for the key secondary AKI endpoint.

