4.1.4 Algorithmic Determinations

4.1.4.1 Reference

Exhibit 1 summarizes the algorithmic determination of reference creatinine. The algorithmic determination of baseline AKI stage will be based on comparing screening creatinine to the reference creatinine determined by Exhibit 1.

Exhibit 1. Algorithmic Determination of Reference Creatinine

Pre processing step:

Creatinine values obtained within 2 days of dosing will be handled as follows:

If there is only one value, this value will be excluded as input to the algorithm below.

If there are more than one value, compare the maximum to the minimum, and if within 25%, then all values will be included as input to the algorithm below. If greater than 25%, then the values obtained within 2 days will be excluded as input to the algorithm below.

This table indicates the rules to be used to determine reference creatinine based on the numbers of historical values available during the last 3 months prior to screening and available 4 to 12 months prior to screening. In general, the algorithm prioritizes use of historical creatinine values obtained within the last 3 months.

Number of last 3 month values	Number of 4 to 12 months	Rule	
0	0 Use MDRD to determine reference creatinine.		
0	1	Use the 4 to 12 month value.	
0 >=2		Use median of 4 to 12 month values.	
1	0	Use <=3 month value.	
>=2	>=0	Use median of <=3 month values.	
1	1	Use the mean of the two available values.	
1	>=2	Use the median of all available values.	
>=2	1	Use the median of all available values.	

The SAS code used to implement the MDRD formula^{5,6} to determine a reference creatinine when no historical values are available is:

```
if sex='Male' and black=0 then do;

t1 = der_age**(-0.203);

t2 = 1;

t3 = 1;

t4 = 186 * t1 *t2 *t3;

Scrt = (75 / t4)**(-0.887);

end;
```

⁵ Levey AS, Bosch JP, Lewis JB, Greene T, Rogers N, Roth D; Modification of Diet in Renal Disease Study Group. A more accurate method to estimate glomerular filtration rate from serum creatinine: a new prediction equation. Ann Intern Med 1999 Mar;130(6):461-470.

⁶ Levey AS, Greene T, Kusek I, Beck G. A simplified equation to predict glomerular filtration from serum creatinine (Abstract). J Am Soc Nephrol 2000;11:155A]

```
if sex='Female' and black=0 then do;
  t1 = der age**(-0.203);
    t2 = 0.742;
    t3 = 1:
    t4 = 186 * t1 * t2 * t3;
     Scrt = (75 / t4) **(-0.887);
     end;
if sex='Male' and black=1 then do;
    t1 = der age**(-0.203);
    t2 = 1;
    t3 = 1.21;

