4.1.4.4 Day 14 eGFR

Day 14 eGFR will be determined by converting Day 14 creatinine to Day 14 eGFR using the following formula:

Day 14 eGFR (mL/min/1.73 m²) = $175 \times (Cr Day 14)^{-1.154} \times (Age)^{-0.203} \times (0.742 if female) \times (1.212 if African American).$

Percentage loss in eGFR at Day 14 will be determined using the following formula.

Percentage loss in eGFR at Day 14 = 100% times [Screening eGFR - (Day 14 eGFR) / Screening eGFR]. If percentage loss $\ge 37\%$ then patient fails the Day 14 endpoint.

4.1.4.5 Determining AKD Stage at Day 28

Exhibit 2 will also be used to determine AKD Stage at Day 28 except that the criterion for renal replacement therapy is an ongoing need rather than initiation.

4.1.4.6 Determining AKD Stage at Day 14

Similarly, Exhibit 2 will be used to determine AKD Stage at Day 14 except that the criterion for renal replacement therapy is an ongoing need rather than initiation.

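### Key secondary renal endpoint: defined as eGFR loss from the patient's reference, but scored by a formula that uses screening eGFR during Stage 2/3 AKI and has a misplaced bracket

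*SAP*

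**What the plan says.** The SAP describes the eGFR loss in three ways.

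- **Definition (1.1, 2.3, 4.1.1).** Success requires survival, freedom from dialysis and less than 37% loss by the MDRD "formula from the patient's reference eGFR)) at Day 28".
- **Scoring formula (4.1.4.3).** "Percentage loss in eGFR at Day 28 = 100% times [Screening eGFR - (Day 28 eGFR) / Screening eGFR", closed by a square bracket. A result of 37% or more fails the endpoint. Section 4.1.4.4 has the same structure for Day 14: "Percentage loss in eGFR at Day 14 = 100% times [Screening eGFR - (Day 14 eGFR) / Screening eGFR".
- **Narrative (2.3, 4.1.1).** The percentage loss "will be based on a comparison of eGFR at screening compared to an algorithmically determined reference creatinine value". This sentence contains no Day 28 value.

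Screening eGFR is not another name for reference eGFR. Section 4.1.4.2 computes it from screening creatinine, while reference creatinine comes from Exhibit 1. The analysis population is restricted: "Only subjects with AKI Stage 2 or Stage 3 prior to initial drug dosing will be included in this comparison". Exhibit 2 sets that stage by comparing screening creatinine with reference. Stage 2 starts at 2 times reference, and Stage 3 at 3 times reference, at 4 mg/dL, or with renal replacement therapy.

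Two further rules refer to reference. Section 2.3 says "A sensitivity analysis will utilize an independently adjudicated reference value to determine baseline eGFR". Section 4.1.4.5 says "Exhibit 2 will also be used to determine AKD Stage at Day 28", and Exhibit 2 is measured against reference.

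**The concern.** The definition asks whether kidney function has returned close to its level before the illness. The formula asks whether it has become much worse than it was at the height of the injury. In patients selected for Stage 2 or 3 injury at screening, these are different questions, and one patient can pass one and fail the other. No sentence in the SAP reconciles them. The protocol cannot settle the matter either: its renal objectives concern KDIGO incidence and recovery, and SAP section 1 says the SAP prevails where the two differ.

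This is the only secondary endpoint with type 1 error control (SAP 2.3 and 5.6). It was added so that this trial could support the AKI trial ATB-203 (SAP 1.1). If the baseline is chosen after unblinding, the confirmatory reading is lost. If the formula is programmed with only its bracket repaired, living patients off dialysis whose kidneys have not recovered are reported as free from durable loss of renal function.

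**Working it through.** The SAP gives no power calculation or worked example for this endpoint, so there is no figure to reproduce beyond the 37% threshold.

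**Inputs.** eGFR = 175 × Cr^-1.154 × age^-0.203 × sex and race factors (4.1.4.2 to 4.1.4.4); failure at a loss of 37% or more (4.1.4.3); Stage 2 from 2 times and Stage 3 from 3 times reference creatinine (Exhibit 2).

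**Step 1: the threshold in creatinine terms.** Within a patient, age, sex and race cancel, so loss = 1 − (creatinine ratio)^-1.154. A 37% loss is a ratio of (1/0.63)^(1/1.154) = 1.492.

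- Against reference, failure starts at 1.49 times reference. At 1.5 times the loss is 37.4%, so the threshold nearly coincides with the Stage 0/1 boundary in Exhibit 2. That match is an inference; the SAP does not say where 37% comes from.
- Against screening (bracket repaired), failure starts at 1.49 times screening creatinine. That is 2 × 1.492 = 2.98 times reference if screened at 2x, and 3 × 1.492 = 4.48 times reference if screened at 3x.

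**Step 2: the same patients under both baselines (bracket repaired).**

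| Screening, × ref | Day 28, × ref | Loss from reference | Loss from screening |
|---|---|---|---|
| 2 | 2 | 1 − 2^-1.154 = 55.1%, fail | 0%, pass |
| 3 | 3 | 1 − 3^-1.154 = 71.9%, fail | 0%, pass |
| 2 | 2.9 | 70.7%, fail | 1 − (2.9/2)^-1.154 = 34.9%, pass |
| 3 | 4.4 | 1 − 4.4^-1.154 = 81.9%, fail | 1 − (4.4/3)^-1.154 = 35.7%, pass |

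By the creatinine ratio, 4.1.4.5 would report the third patient as AKD Stage 2 and the fourth as Stage 3, while the endpoint counts both as successes. Whenever screening creatinine exceeds reference, disagreements run one way only: fail by definition, pass by formula.

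**Step 3: the bracket as printed.** It reads Screening − (Day 28/Screening), not (Screening − Day 28)/Screening. Take an assumed non-black man aged 60 screened at 3.0 mg/dL. His eGFR is 21.45 at 3.0 mg/dL and 76.22 at 1.0 mg/dL.

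- Unchanged at 3.0: 100 × (21.45 − 21.45/21.45) = 2045%, fail.
- Recovered to 1.0: 100 × (21.45 − 76.22/21.45) = 1790%, fail.

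A literal pass needs Day 28 eGFR above S × (S − 0.37), where S is screening eGFR. For this man that means Day 28 creatinine below 0.09, 0.21, 0.38 or 0.60 mg/dL at screening values of 2, 3, 4 or 5 mg/dL. At 8 mg/dL the limit is 1.57, so the printed formula does not fail everyone.

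**Step 4: the other rules.** The adjudicated-reference sensitivity analysis cannot change any patient's percentage loss under 4.1.4.3, because that formula has no reference term. Section 4.1.3 treats improvement to a lower stage, but no better than Stage 1, as a separate exploratory outcome. Under a screening baseline, any fall in creatinine gives a negative loss and already meets the eGFR criterion for full freedom.

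**Separate minor point.** When there is no historical creatinine, the code under Exhibit 1 sets reference at eGFR 75 using the constants 186, −0.887 and 1.21. The later equations use 175, −1.154 and 1.212. Converted back with those equations, the imputed reference gives eGFR 69.9 to 71.0 over ages 20 to 80 and all four sex and race groups. Reference creatinine is therefore 4.8% to 6.3% too high compared with exact inversion at 75.

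**The case against.** The endpoint plays no part in study success (SAP 2.2) and is confirmatory only if NICCE reaches p≤0.01 and CCPE p≤0.05. That is true, and it limits the consequence.

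The bracket is plainly a typing slip. A result of 2045% would be noticed and corrected, so Step 3 describes code that would probably not survive. That is fair. The baseline is the more serious defect because it remains after the bracket is repaired.

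The supporting rules are not decisive by themselves. AKD stage is a separate exploratory outcome, and measuring it against reference does not dictate the baseline of the percentage loss. The adjudicated-reference analysis is not empty under a screening baseline, because it changes who counts as Stage 2 or 3 (SAP Appendix 1, Tables 14.2.6.2.2 and 14.2.6.2.4). Both points stand: these rules fit a reference baseline better but do not prove it. The case rests on the definition, stated three times, and on the sensitivity wording that ties baseline eGFR to the reference.

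Not every unresolved injury is passed. A patient screened at 2x and at 3.5x on Day 28 has lost 47.6% from screening and fails either way. The Stage 2 label at 2.9x also needs a reference below about 1.38 mg/dL (4/2.9), since 4 mg/dL may be Stage 3.

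Finally, the endpoint is meant to match ATB-203, whose formula is not in these documents. That is a reason to check the wording against ATB-203 before finalising it.

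**Conclusion.** The concern holds. The SAP defines the loss from reference, scores it from screening, and adds a third description with no Day 28 value. Even with the bracket repaired, a patient who is alive, off dialysis and below 1.49 times screening creatinine at Day 28 is a success, including one with no recovery from 2 or 3 times reference (0% against 55.1% or 71.9%). With the bracket taken literally, full recovery can score as failure.

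The creatinine-ratio results depend only on the SAP's own exponent and threshold; the literal-bracket figures assume the patient described. The share of patients affected cannot be computed, because the documents give no Day 28 creatinine data. NICCE, CCPE and overall study success are untouched. This must be fixed before unblinding because it is the only type-1-error-controlled secondary endpoint. The imputation constants are a minor, separate matter.

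**What to change.** In SAP 4.1.4.3 and 4.1.4.4 write: loss = 100 × (Reference eGFR − Day X eGFR) / Reference eGFR, where Reference eGFR = 175 × (reference creatinine)^-1.154 × age^-0.203 × (0.742 if female) × (1.212 if African American).

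In 2.3 and 4.1.1 replace the sentence that compares screening with reference by one that compares eGFR at Day 14 or Day 28 with the eGFR at the algorithmically determined reference creatinine. Keep the adjudicated-reference sensitivity analysis, which then does what it says. Confirm the result against the ATB-203 definition, since the two are meant to agree.

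Separately, for patients with no historical creatinine, obtain the reference by inverting the same 175-based equation at eGFR 75, again after checking ATB-203.

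The cost is SAP wording and a few lines of SAS before unblinding. No new data are needed.

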4.1.4.4 Day 14 eGFR

Day 14 eGFR will be determined by converting Day 14 creatinine to Day 14 eGFR using the following formula:

Day 14 eGFR (mL/min/1.73 m²) = $175 \times (Cr Day 14)^{-1.154} \times (Age)^{-0.203} \times (0.742 if female) \times (1.212 if African American).$

Percentage loss in eGFR at Day 14 will be determined using the following formula.

Percentage loss in eGFR at Day 14 = 100% times [Screening eGFR - (Day 14 eGFR) / Screening eGFR]. If percentage loss $\ge 37\%$ then patient fails the Day 14 endpoint.

4.1.4.5 Determining AKD Stage at Day 28

Exhibit 2 will also be used to determine AKD Stage at Day 28 except that the criterion for renal replacement therapy is an ongoing need rather than initiation.

4.1.4.6 Determining AKD Stage at Day 14

Similarly, Exhibit 2 will be used to determine AKD Stage at Day 14 except that the criterion for renal replacement therapy is an ongoing need rather than initiation.

4.1.4.7 Alternative Algorithmic Determination of Day 28 Creatinine

If Day 28 creatinine is missing, LOCF will be used to impute Day 28 creatinine in primary analyses. As a sensitivity analysis, the following alternative approach to determining the recovery creatinine is as follows.

1. Take all creatinine values between day 14 and day 28 and determine if they are consistent –if high and low value in the range are different by >50% (example 1.0 and 1.6) flag as "unstable"

- 2. If unstable, take the LAST value in the range as the recovery creatinine.
- 3. If not unstable, take the MEAN of all values in the 14-28 day range as the recovery creatinine.

4.1.5 Processing of Adjudicated AKI Data

Three independent adjudicators will determine:

- Reference Creatinine
- Maximal AKI Stage (over first seven days)
- AKD Stage at Day 14

The adjudicated reference will be the mean of the three adjudicated values.

The adjudicated Maximal AKI Stage and AKD Stage at Day 14 will be determined through 'vote counting'.

Independent adjudication of AKD stage will be used to determining Achieving Freedom from Durable Loss of Renal Function at Day 14 and Improvement in Durable Loss of Renal Function at Day 14 in sensitivity analyses.

4.2 Primary Endpoint Components and Other mSOFA Related Outcomes

The primary endpoint components and other mSOFA related outcomes will be evaluated as additional secondary efficacy endpoints in descriptive treatment group comparisons using the statistical methods summarized below.

- Distribution of mSOFA scores at Day 14
- Kaplan-Meier analysis of the time to resolution of mSOFA score to ≤ 1 with censoring at Day 14
- Kaplan-Meier analysis of the time to resolution of mSOFA score to ≤ 1 up to Day 28
- Single components of the primary composite end point:
 - o Alive at Day 28
 - o Debridements by Day $14 \le 3$
 - Number of amputations (removal of a limb or portion of a limb to the level of a joint space) (done after first debridement)
 - o mSOFA score on Day $14 \le 1$
 - o Reduction of ≥3 score points between baseline and Day 14 mSOFA score.
- Clinical local parameters:
 - Number of debridements to days 7, 10, and 14 Proportion of patients needing (up to Day 14):
 - only one debridement to control the infection
 - 2 debridements to control the infection
 - 3 debridements to control the infection
 - \geq 3 debridements to control the infection
 - >3 debridements to control the infection

- Clinical systemic parameters:
 - Evaluation of organ function over time, using mSOFA score (total score and organ specific score)

4.3 Critical care and hospital stay parameters

The following critical care and hospital stay parameters will be measured up to Day 28. These parameters relate to medical and procedures costs:

- o ICU free days
- o Days in ICU
- o Days on ventilator
- Ventilator free days
- Vasopressors days/ Vasopressors free days
- Hospital length of stay (days)

Outcomes like duration of mechanical ventilation and incidence of organ failure may be lower in the group with higher mortality simply because of the competing effect of mortality (Rubenfeld, Angus et al. 1999⁷). Patients who die are not at risk to develop further organ failures or prolonged ventilator dependence. One proposed solution to this problem is to calculate life-support-free days. For example, ventilator-free days can be calculated over a predefined measurement period of (typically) 28 days. Patients who die or are mechanically ventilated longer than this period are assigned zero ventilator-free days for any days on which the patient is not alive or any day beyond the 28 days. All survivors accrue one ventilator-free day for each day after entry into the study that they are both alive and free of mechanical ventilation. By combining mortality and morbidity in one measure, the free-day outcome avoids the problem of competing mortality. A similar approach will be used to determine ICU-free days and vasopressors free days.

The 28-day horizon will be used when determining ICU-free days, vasopressor-free days, and mechanical ventilation-free days. ICU time will be calculated using calendar days starting on the day of admission to the ICU and ending on the day of ICU discharge inclusive.

A vasopressor-free day or ventilator-free day will be defined based on a calendar days starting from the day of drug administration. Any day upon which a patient experienced no part of a calendar day on a vasopressor or a ventilator is a ventilator/vasopressor free day. For example, if the patient was on a ventilator for one hour on any given day, or for even one minute, this day will not count as a ventilator-free day. The same method will be used in calculating vasopressor-free days; a vasopressor-free day means a day alive and not on a vasopressor at any time during that day. This method is a convention generally accepted for these parameters. Events that occur under general anesthesia are not counted. Hospital length of stay will be calculated according the total number of calendar days in the hospital.

⁷ Rubenfeld GD, Angus DC, et al. Outcomes reserach in critical care. Am J Respir Crit Care Med 1999: 160(358-367).

The table summarizing critical care related outcomes will also be presented stratified according to the set of baseline covariate stratified analyses defined below. In addition, critical care related outcomes will be similarly summarized and compared between patients with NICCE success and NICCE failure.

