5.7 Descriptive Analyses of Additional Secondary Endpoints

Additional secondary endpoints have been specified from several domains including individual components of the primary composite endpoint (NICCE), time to resolution of organ dysfunction, critical care and hospital stay parameters (ICU and ICU-free days, ventilator days and -free days, vasopressor days and -free days, hospital LOS), clinical local parameters (debridement history variables), and clinical systemic parameters (mSOFA over time, incidence and recovery from AKI). Analyses for these endpoints will generally be descriptive, with emphasis on characterizing clinical effect sizes¹⁵. Nominal p-values will be presented in some cases as an aid to interpretation but with no adjustment for multiplicity. Categorical outcomes will be summarized using counts and percentages with nominal p-values determined through chi-square or exact methods. Critical care and hospital stay endpoints will be compared using non-parametric approaches including using concordance statistics (c-stat) to characterize clinical effect size and Wilcoxon rank sum tests to determine nominal statistical significance. The c-stat is the probability that a randomly selected patient treated with Reltecimod has a better (e.g., greater number of free-days) than a randomly selection patient treatment with placebo. Methods appropriate for time-to-event endpoints including survival and life-table methods will be used for time-to-organ dysfunction resolution endpoints. Additional analyses of mSOFA over time will employ methods appropriate for longitudinal data. For these analyses, statistical testing and estimation will be based on a Mixed Model Repeated Measures (MMRM)¹⁶.

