8.8 MMRM Analyses

Figure 17 will be a line graph of least squares predicted mean values over time based on the mixed model for repeated measures (MMRM). This figure will summarize the MMRM results for values over time.

Figure 18 will be a line graph of least squares predicted mean change values over time based on the mixed model for repeated measures (MMRM). This figure will summarize the MMRM results for values over time.

8.9 Critical care and hospital stay parameters, to be measured until Day 28

The following critical care and hospital stay parameters will be assessed in the mITT analysis set.

- o ICU free days
- o Days in ICU
- Days on ventilator
- Ventilator free days
- Vasopressors days
- o Vasopressors free days
- Hospital length of stay (days)

Because of the expected skewness in the distributions of these parameters, non-parametric Wilcoxon rank sum tests will be used assess the statistical significance of treatment group differences in these parameters. Table 14.2.4.1 will provide summary statistics by treatment groups including mean, median, standard deviation, 25th percentile, 75th percentile, minimum, and maximum values. Analyses will focus on clinical effect sizes. The non-parametric clinical effect size to be used is the concordance statistic (c-stat) determined from a logistic regression. The c-stat is the probability that a randomly selected subject treated with Reltecimod has a better outcome (e.g., more free-days) than a randomly selected placebo subject and is related to the area under a receiver operating characteristic (ROC) curve²⁵. Graphical comparisons of distributions between treatment groups will be provided using box and whiskers plots (Figures 19 to 25).

Table 14.2.4.2 will summarize hospital discharge status in the mITT analysis set.

Table 14.2.4.3 will summarize hospital readmissions in the mITT analysis set.

Table 14.2.4.4 will summarize critical care and hospital stay parameters over days 1 to 28 comparing NICCE successes to NICCE failures. Figures 26 to 33 will graphically compare these distributions using box and whiskers plots.

²⁵ Hanley JA and McNeil BJ. The Meaning and Use of the Area under a Receiver Operating Characteristic Curve (ROC), Radiology 1982: 143: 29-36.

Additional graphical analyses will include displaying the percentages of patients staying in the ICU, needing ventilation, and staying in the hospital over time by treatment group (Figures 34, 35, and 36).

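### Hospital length of stay is tested as a raw day count with no rule for death, so an early death ranks as a short, favourable stay

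*SAP*

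**What the plan says.** SAP 4.3 lists seven critical care and hospital stay parameters measured up to Day 28: days in ICU, on ventilator and on vasopressors, a free-day version of each, and hospital length of stay. It says that outcomes of the duration type "may be lower in the group with higher mortality simply because of the competing effect of mortality". It describes ventilator-free days as the remedy, with no credit for days on which the patient is not alive, and then extends it: "A similar approach will be used to determine ICU-free days and vasopressors free days". Hospital stay is left out of that extension: "Hospital length of stay will be calculated according the total number of calendar days in the hospital".

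SAP 8.9 analyses all seven parameters in the mITT set: "non-parametric Wilcoxon rank sum tests will be used assess the statistical significance of treatment group differences in these parameters". It adds a concordance statistic as the clinical effect size: "The c-stat is the probability that a randomly selected subject treated with Reltecimod has a better outcome". The only illustration of a better outcome is a larger number of free days.

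SAP 5.7 sets the status of these endpoints: "Nominal p-values will be presented in some cases as an aid to interpretation but with no adjustment for multiplicity".

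**The concern.** For a raw day count, a better outcome can only mean fewer days. A patient who dies in hospital on Day 2 then has a two-day stay and outranks almost every survivor. SAP 4.3 identifies this mechanism and corrects it for three resources, but for hospital stay the mITT analysis has no version that takes account of death.

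At stake is the direction of a secondary result. Hospital length of stay is a secondary objective in Protocol 2.2 and a health-economic item in Protocol 7.3. Its table is repeated for subgroups 1 to 11 (SAP 4.6) and in the per-protocol set (SAP 8.9). A difference in mortality alone could make the arm with more deaths look better on hospital stay.

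**Working it through.** **No planned figure to reproduce.** The documents give no power, effect size or mortality assumption for the stay endpoints.

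**How the plan treats death, measure by measure.**

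| Resource | Raw days tested | Death-aware version |
|---|---|---|
| ICU | yes | ICU-free days |
| Ventilator | yes | ventilator-free days |
| Vasopressor | yes | vasopressor-free days |
| Hospital | yes | none |

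Elsewhere the SAP does state a rule: in the Day 14 time-to-resolution analysis (SAP 8.7), patients who die are treated as never having resolved.

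**Inputs.**
- Mortality 20% vs 6.7%: Phase 2 placebo and 0.5 mg/kg arms (Protocol 1.1.3.3.2, Table 3).
- 145 patients per arm (SAP 2.4.1).
- Assumed, because the documents give nothing: survivor stay is gamma (shape 2.2, scale 7 days) capped at 28, the same in both arms. All deaths occur in hospital. Death times are either early (gamma, shape 1.5, scale 3, mean 4.5 days) or spread evenly over 28 days.

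**Formula.** Let p1 and p2 be the higher and lower mortality. Let q be the probability that a death outranks a survivor, with ties counted as half. When survivors are alike in both arms, the c-statistic for the arm with more deaths is

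c = 0.5 + (p1 − p2)(q − 0.5).

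Here p1 − p2 = 0.20 − 0.067 = 0.133. The two raw-day values of q come from simulating the assumed distributions.

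| Scoring | q | c |
|---|---|---|
| Raw days, every death before every discharge (bound) | 1 | 0.5 + 0.133 × 0.5 = 0.567 |
| Raw days, early deaths | 0.876 | 0.5 + 0.133 × 0.376 = 0.550 |
| Raw days, deaths spread evenly | 0.511 | 0.5 + 0.133 × 0.011 = 0.501 |
| Hospital-free days | 0.057 | 0.5 − 0.133 × 0.443 = 0.441 |
| Deaths ranked worst | 0 | 0.5 − 0.133 × 0.5 = 0.434 |

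For hospital-free days, in-hospital deaths tie with survivors whose stay reaches the 28-day cap. These are about 11.5% of survivors, so q = 0.115 / 2. Direct simulation with 400,000 patients per arm agrees with every row except the bound, which was not simulated, to within 0.002. With equal mortality of 15% in both arms, every scoring gives 0.50.

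**Smaller mortality gaps, early deaths.** For 10% vs 2%: 0.5 + 0.08 × 0.376 = 0.530 raw, against 0.46 with deaths ranked worst. For 17% vs 10%: 0.5 + 0.07 × 0.376 = 0.526, against 0.465. These pairs are assumptions.

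**Longer stays.** With a survivor median of 18 days and 20% vs 6.7% mortality, simulated trials of 145 per arm gave raw c = 0.562 for early deaths (mean day 4) and 0.522 for deaths spread evenly. Hospital-free days gave 0.449 and 0.451.

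**Against sampling error.** The null standard error of c is √[(2n + 1)/(12n²)] = √(291/252,300) = 0.034. A true c of 0.55 is 0.05/0.034 = 1.47 standard errors from 0.5. The chance of nominal p < 0.05 in favour of the arm with more deaths is then P(Z > 1.96 − 1.47) ≈ 0.31. In the longer-stay simulation it was 44.5% with early deaths and 9.6% with deaths spread evenly.

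**The case against.** A reader might infer that ICU, ventilator and vasopressor days are affected in the same way. The documents do not support that. Each has a free-day companion in the same table. Inclusion requires mSOFA of at least 3, not ICU admission, so survivors with no ICU, ventilator or vasopressor days score zero and outrank an early death. Simulations at 20% vs 6.7% gave raw c for the higher-mortality arm of 0.46 to 0.553 for ICU days, 0.476 to 0.512 for ventilator days and 0.469 to 0.518 for vasopressor days. In several scenarios the raw count already favoured the arm with fewer deaths.

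Other points against the concern:

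- The SAP nowhere instructs that deaths rank as favourable. That follows from the day count and the missing rule.
- The size depends on death timing, which the documents do not give. With deaths spread evenly and the shorter stay distribution, the wrong-way effect nearly vanishes.
- Phase 2 shows no reversal: placebo had more deaths and also more ICU days (8.9 vs 5.4) and ventilator days (5.2 vs 2.7). That study was small, and its Table 3 does not report hospital stay.
- The per-protocol set excludes deaths within one day of dosing (SAP 2.6), and the protocol allows restriction to patients surviving at least three days (Protocol 9.2.2). Both are optional and partial, and neither touches the mITT analysis.
- Mortality and discharge status are reported separately, and SAP 4.3 ties these parameters to costs, for which raw days are a legitimate quantity.

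These points narrow the concern to hospital stay and limit its weight. They do not supply a death rule for it. Even in the mildest case, raw days give about 0.50 where a death-aware measure gives 0.43 to 0.44.

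**Conclusion.** The concern holds for hospital length of stay. It is the one stay measure with no death-aware version, and it still receives a p-value and a statistic labelled as the probability of a better outcome. At 20% vs 6.7% mortality with identical survivors, c for the arm with more deaths is about 0.50 to 0.55, and 0.52 to 0.56 if stays are longer. With death counted as a bad outcome it is about 0.43 to 0.44 (up to 0.45 for hospital-free days with longer stays). Stay distributions and death timing are assumed; the mortality pair is from Phase 2.

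The bias does not inherently favour the drug. If mortality falls on Reltecimod as in Phase 2, placebo is the higher-mortality arm and the c-statistic for Reltecimod would read as low as 1 − 0.55 = 0.45.

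A reader might also infer that the trial's conclusions are at risk. They are not: these endpoints are descriptive, have nominal p-values, and lie outside the success criterion (SAP 2.2) and the type 1 error control (SAP 5.6).

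**What to change.** In SAP 4.3 and 8.9, add hospital-free days to Day 28: days alive and out of hospital, with deaths handled as in the other free-day measures. State the day on which counting starts and whether readmission days count as hospital days. Apply the Wilcoxon test and c-statistic to this measure.

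Let the four free-day measures carry the nominal p-values and c-statistics. Report raw hospital, ICU, ventilator and vasopressor days as descriptive summaries only. Ranking deaths worst within the three raw measures that already have a free-day version would largely duplicate those analyses and is not needed.

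The cost is SAP wording and one derived variable from hospital stay, readmission and death data already collected. The SAP is to be finalised before unblinding, so the change can be made without knowledge of treatment. The downside is that the hospital-stay comparison will also reflect mortality, and raw days will serve only as a description of resource use.
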